8.1 Funding Source

At this time, there is no funding for this research study. It will be conducted using existing resources.

8.2 Conflict of Interest

Neither the investigator, nor any of his designees have any conflicts of interest related to this study.

Official Title: **ATIVO Study – Anticoagulation Therapy in the Very Old**

NCT #: **03103763**

Statistical analysis plan

For the purpose of this study, we attempted to detect differences in outcomes among age groups (70-79, 80-89, and 90+) undergoing anticoagulation therapy at study enrollment and in 6-month intervals for 24 months. Descriptive statistics were used to summarize the demographic (age group, sex, and living arrangement) and clinical characteristics (mobility, alcohol use, CHADS2-VASc, Fragility score, mini Cog, and mobility scale) of patients included in the study, with continuous variables presented as a mean +- standard deviation and categorical variables as frequencies/percentages of the total. The primary outcome of interest was time in therapeutic range (TTR), a percentage of time that a patient's International Normalized Ratio (INR) values were in range over a 6-month period. Secondary outcomes were all-cause mortality, stroke, and major bleeding events. Student t tests and chi-squared tests were conducted to compare data between groups. Statistical significance was set at $P < .05$ with a 95% confidence interval.

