4.3 Subject Recruitment and Screening

Subjects will be recruited from the PBMC Anticoagulation Services (ACS) department. The medical records used by the ACS will be searched using age ≥ 70 and diagnosis of atrial fibrillation as search criteria. All patients aged 90 years or older who fit the criteria will be approached about participation in the study.

An equal number of patients from the ACS who are aged 80-89 years and, an equal number of patients from the ACS will be enrolled who are aged 70-79 years will be enrolled.

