5.4 Assessments

Mini-Cog™ (used by permission) is a validated screening tool used to detect dementia.⁵

CHA₂DS₂-VASc score is a validated tool for stroke risk stratification.³

HAS-BLED score is a validated schema for risk stratification for bleeding events among anticoagulated patients.¹

Dalhousie University Clinical Frailty Scale is a simplified scale to assess frailty.⁴

Mobility score is a simple noting of patient mobility at each visit- ambulating without assist, ambulating with cane, ambulating with walker, or arrived in wheelchair.

Time in Therapeutic Range (TTR) will be calculated utilizing the Rosendaal method of percentage days in therapeutic range in the past 6 months.

6 Analysis Plan

Compare by decade:

Sex

Living arrangement

Alcohol use

CHA2DS2-VASc score

HAS-BLED score

Dalhousie University Clinical Frailty Scale

Mobility score

TTR for 2 years and best and worse 6 months

Death secondary to anticoagulation

Death secondary to cardiovascular causes

Number of hospitalizations

Major bleeding defined as any bleeding meeting at least one of the following criteria:

- Fatal bleeding
- Symptomatic bleeding in a critical area or organ, such as intracranial, intraspinal, intraocular, retroperitoneal, intraarticular or pericardial or intramuscular with compartment syndrome, and/or
- Bleeding causing a fall in hemoglobin level of 2 g/dl or more, or leading to transfusion of two or more units of whole blood or red cells.²

CNS Bleeds with death, disability, or no disability

Embolic ischemic stroke

Non embolic ischemic stroke

Mechanism unknown ischemic stroke

Hemorrhagic stroke non traumatic

Traumatic intracerebral hemorrhage

Traumatic subdural hemorrhage

Cardiovascular events (non stroke type)

7 Confidentiality

Subject information will be kept in the PBMC Clinical Research office which is locked when unattended. Information entered into a database will be housed on a PBMC shared drive which is password protected. Information about study subjects will be kept confidential and managed according to the requirements of the Health Insurance Portability and Accountability Act of 1996 (HIPAA).

- Protected health information (PHI) which will be collected from subjects in this study include, demographics, medical history, medication list, information related to adverse events, symptoms related to atrial fibrillation and the use of anticoagulants.
- The investigator and his designees will have access to this information.

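### No sex-adjusted comparison of the age groups is planned, so the contrasts by decade may be confounded by sex if the sex mix differs between decades

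*SAP*

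**What the plan says.** The SAP states its aim as follows: "we attempted to detect differences in outcomes among age groups (70-79, 80-89, and 90"+). The primary endpoint is TTR over a 6-month period: "The primary outcome of interest was time in therapeutic range (TTR"). For the rest, "Secondary outcomes were all-cause mortality, stroke, and major bleeding events".

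Sex appears twice. In Protocol Section 6 it is an item under "Compare by decade". In the SAP it is a baseline characteristic to be summarised: "Descriptive statistics were used to summarize the demographic (age group, sex, and living arrangement").

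The only inferential methods named are these: "Student t tests and chi-squared tests were conducted to compare data between groups". The threshold is also given: "Statistical significance was set at $P < .05$ with a 95% confidence interval". Neither document names a regression model, covariate, stratified test or standardisation.

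Protocol Section 4.3 sets the make-up of the groups. For the oldest, "All patients aged 90 years or older who fit the criteria will be approached". The two younger groups are then filled to the same number. No matching or quota on sex is described. Protocol Section 3 calls the study a prospective registry, so nothing is randomised.

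**The concern.** Equal group sizes do not balance any characteristic other than the count. If one decade contains more women than another, and women and men differ in INR control or event risk, the crude difference between the decades includes a contribution from sex. That contribution could imitate an age difference or hide one. Tabulating sex by decade, or testing it with a chi-squared test, would show the imbalance but would not take it out of the outcome tests.

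This matters because the study goes beyond description. Protocol Section 2 also sets out to find factors that stand in the way of safe and effective anticoagulation, and the SAP tests age differences for significance. A significant contrast between the oldest and youngest groups will tend to be read as an effect of age.

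Sex is a natural first adjustment variable. It is not a consequence of ageing, so adjusting for it does not remove part of an age effect that acts through it. Frailty, mobility and cognition are different: they may lie on the path from age to outcome, and leaving them out of the comparison is easier to defend.

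**Working it through.** The documents state no sample size, standard deviation, event rate or sex distribution. There is no figure of the plan's to reproduce, and every input below is an assumption.

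**Assumed inputs**
- Gap in the share of women, oldest versus youngest group: 0 to 30 percentage points, with up to 35 as a wider case.
- Share of women in the youngest group: 45%.
- Difference in TTR between the sexes: 0 to 6 points.
- Risk ratio between the sexes for an event: 1.0 to 2.0.
- Standard deviation of TTR: 20 points.
- Patients per group (n): 30, 100 or 200.

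**Shift in the crude TTR contrast** = gap × sex difference in TTR
- No gap or no sex difference: 0.
- 0.20 × 4 = 0.8 points.
- 0.25 × 4 = 1.0 point.
- 0.30 × 6 = 1.8 points.
- Wider case: 0.35 × 6 = 2.1 points.

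**Multiplier on the crude risk ratio** = [1 + p1(RR − 1)] / [1 + p0(RR − 1)], where p1 and p0 are the shares of women in the oldest and youngest groups and RR is the risk ratio between the sexes
- No gap, or RR = 1: 1.00.
- p1 = 0.70, p0 = 0.45, RR = 1.3: 1.21 / 1.135 = 1.07.
- p1 = 0.65, p0 = 0.45, RR = 1.5: 1.325 / 1.225 = 1.08.
- p1 = 0.75, p0 = 0.45, RR = 2.0: 1.75 / 1.45 = 1.21.

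These figures take the sex that is commoner in the oldest group to have the higher TTR or risk. In the opposite case the TTR shift changes sign and the multiplier falls below 1. The documents do not settle the direction.

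**Effect on the test of TTR.** Suppose age has no effect and the crude contrast is shifted by 1.2 points (for example 0.30 × 4). With d = 1.2 / (20 × √(2/n)), the two-sided rejection rate at nominal 0.05 is Φ(d − 1.96) + Φ(−d − 1.96).

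| n per group | d | Rejection rate |
|---|---|---|
| 30 | 0.23 | 0.056 |
| 100 | 0.42 | 0.071 |
| 200 | 0.60 | 0.092 |

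The SAP does not say whether its tests are two-sided; that is assumed here.

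**The case against.** The strongest reply is that the crude contrast is a legitimate target. A registry that asks how this clinic's patients aged 90 or above fare beside those in their 70s is answered by the unadjusted difference. Adjustment answers another question: how the decades would differ with the same sex mix. This stands, and it is why the crude result should be kept. It does not dispose of the point, because the risk-factor objective in Protocol Section 2 needs more than a description.

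A reader might infer from the listing of sex in Protocol Section 6 that the plan expects it to differ by decade. The text does not support that. The same list includes alcohol use, hospitalisations, deaths and stroke types, and it states no direction or size for any of them. Nor do the documents say that the oldest group in this clinic has more women.

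Two further replies stand in part. Any imbalance would be visible, since sex is to be reported by decade, although seeing it does not remove it. And adjusting for sex would not deal with selection by survival to 90, or with other characteristics that differ between decades.

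**Conclusion.** The gap in the plan is confirmed: groups that are not randomised and are equal only in number are compared without adjustment, although sex is on record. The consequence is conditional. Confounding by sex needs both a different sex mix between decades and a relation between sex and the outcome, and the documents establish neither. A reader might conclude that the age effect on TTR, stroke and bleeding is in fact mixed with a sex effect; the documents support only that it may be.

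Under the assumed inputs the shift is about 0 to 2 TTR points, or a risk-ratio multiplier of about 1.0 to 1.2. It is zero if either condition fails. With no sample size or event rate documented, no particular conclusion can be shown to change. The correction is worth making because it costs little, and not because a large bias has been demonstrated.

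**What to change.** Keep the crude comparison and describe it as the difference between decades as they present in the clinic. Report beside it a comparison of the age groups adjusted for sex:

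- TTR: linear regression with age group and sex.
- Death, stroke and major bleeding: a Mantel-Haenszel analysis stratified by sex, or logistic or Poisson regression with age group and sex where event counts allow.

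State which of the two results answers which question. The SAP is written in the past tense, so if the analysis has already been done, label the adjusted result as added after the plan.

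Sex is already collected, so no new data are needed. The cost is slightly more analysis work. If strokes or major bleeds are few, the adjusted estimates will be imprecise and should be presented as such.

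### The SAP names an undefined stroke outcome and all-cause mortality where Protocol Section 6 lists four stroke types and two cause-specific deaths, and does not link the two lists

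*SAP*

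**What the plan says.** Protocol Section 6 (Analysis Plan) opens with "Compare by decade" and then gives a list in which no item is ranked primary or secondary. Six items matter here:

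- two deaths by cause: "Death secondary to anticoagulation" and "Death secondary to cardiovascular causes";
- four items named as stroke: "Embolic ischemic stroke", "Non embolic ischemic stroke", "Mechanism unknown ischemic stroke" and "Hemorrhagic stroke non traumatic".

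The same section defines major bleeding. The definition takes in fatal bleeds and symptomatic bleeds at critical sites, intracranial ones included.

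The SAP is one paragraph. It makes TTR the primary outcome and continues: "Secondary outcomes were all-cause mortality, stroke, and major bleeding events". Groups are compared with t tests and chi-squared tests. The SAP does not say what counts as a stroke, mentions no cause of death and does not cite Section 6.

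**The concern.** Protocol Section 2 sets out to evaluate both how well and how safely warfarin works in the very old. The Introduction reports preliminary data in which clotting and bleeding complications are both more frequent in that group. Section 6 is built to show the two kinds of event separately by decade. A reader of the SAP cannot tell whether its stroke outcome is ischemic only or ischemic plus hemorrhagic, and the death most directly tied to treatment safety has no line of its own.

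At stake is how well the secondary outcomes answer the objective. They are the only clinical efficacy and safety events that the SAP names.

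**Working it through.** The documents give no sample size, event count or event rate, so there is no stated figure to reproduce. The check is a comparison of texts, followed by what can and cannot be recovered from the SAP's outcomes.

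**Step 1: count the items.** Section 6: 4 stroke types + 2 cause-specific deaths = 6. SAP: stroke + all-cause mortality = 2.

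| Section 6 item | Nearest SAP outcome | Recoverable from it? |
|---|---|---|
| Ischemic stroke, three types | Stroke (undefined) | Types: no. Total: only if stroke means ischemic |
| Non-traumatic hemorrhagic stroke | Stroke (undefined), major bleeding | Not as its own count |
| Anticoagulation death | All-cause mortality | No |
| Cardiovascular death | All-cause mortality | No |

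All-cause mortality is a new outcome. It includes deaths from other causes, so it is not the sum of the two Section 6 deaths.

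**Step 2: the two readings of stroke.**

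- *Ischemic only.* Stroke and major bleeding then form an efficacy and safety pair. Nothing is mixed, but the three ischemic types are still not shown and the SAP does not say that this is what it means.
- *All four types.* In one age group let S be strokes, I ischemic strokes, H hemorrhagic strokes and M major bleeds. Only S and M are reported. If every hemorrhagic stroke is symptomatic, it meets the major bleeding definition and H is at most M. All that follows is that I lies between max(0, S − M) and S. M also contains bleeds outside the brain, so this range can be wide.

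**Step 3: can mixing matter?** This is an illustration on assumed values only. For 90+ against 70-79, with h the hemorrhagic share of strokes at 70-79:

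pooled ratio = (1 − h) × ischemic ratio + h × hemorrhagic ratio

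- Ischemic 2.0, hemorrhagic 2.0, any h: 2.0.
- Ischemic 1.5, hemorrhagic 4, h = 0.2: 0.8 × 1.5 + 0.2 × 4 = 2.0.

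The same pooled ratio fits two different pictures. Over ischemic ratios of 1.5 to 2.0, hemorrhagic ratios of 1.5 to 4 and h of 10% to 30%, the pooled ratio runs from 1.5 to 2.6:

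- lowest relative to ischemic: 0.7 × 2.0 + 0.3 × 1.5 = 1.85, or 0.93 times the ischemic ratio;
- highest relative to ischemic: 0.7 × 1.5 + 0.3 × 4 = 2.25, or 1.5 times;
- highest overall: 0.7 × 2.0 + 0.3 × 4 = 2.6.

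When the two ratios are equal there is no distortion.

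**Step 4: precision and testing with sparse counts (assumed counts).** Exact (Clopper-Pearson) 95% intervals: 0 of 50 gives 0 to 7.1%; 0 of 100 gives 0 to 3.6%; 4 of 100 gives 1.1% to 9.9%.

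- *0 against 4 of 50.* Expected events are 2 per group. Chi-squared (uncorrected) = 8/2 + 8/48 = 4.17, P = 0.041. Fisher P = 2 × C(50,4)/C(100,4) = 2 × 230,300/3,921,225 = 0.117.
- *0, 0 and 3 of 50.* Expected events are 1 per group. Chi-squared = 6/1 + 6/49 = 6.12 on 2 degrees of freedom, P = 0.047. Freeman-Halton P = 3 × C(50,3)/C(150,3) = 58,800/551,300 = 0.107.

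At counts this small, the planned test can fall below 0.05 when the exact test does not.

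**The case against.** **The SAP omits; it does not withdraw.** A reader might infer that the SAP replaces the six items. The documents do not support that. Section 6 is itself an analysis plan, and nothing in the SAP cancels it. If both texts stand, the subtypes and cause-specific deaths are still due. This objection holds. What remains is that the SAP gives those items no stated analysis and does not link itself to Section 6.

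**Pooling is only one reading.** The Introduction uses stroke for the clot-related event and sets it against major hemorrhage, which favors an ischemic-only meaning. Section 6 uses the same word for a hemorrhagic event. The term is ambiguous, and mixing can only be stated as a conditional.

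**Hemorrhagic harm is not lost.** A reader might infer that bleeding by age group disappears. It does not: major bleeding is a separate SAP outcome and captures fatal and symptomatic intracranial bleeds. The loss is narrower, namely the ischemic count and hemorrhagic stroke as a distinct part of bleeding.

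**Overlap is not double counting.** On the all-types reading a fatal hemorrhagic stroke counts in all three secondary outcomes. These are separate outcomes, not a composite, and Section 6 overlaps in the same way. The overlap needs stating; it is not a defect.

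**All-cause mortality is defensible.** Section 5.2 lets outcomes come by phone, from records, or from relatives or friends, and the protocol describes no adjudication of cause of death. That supports keeping all-cause mortality, but not leaving out the attributed deaths without comment.

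**Conclusion.** The point holds as a gap in definition and reporting. Six Section 6 items correspond to two SAP outcomes, with no definition of stroke, no reference to Section 6 and no reason given. If stroke covers all four types, the ischemic count by age group cannot be read. On either reading, deaths attributed to anticoagulation are not shown. The efficacy and safety objective is therefore answered less well than Section 6 allows. TTR is unaffected.

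The size of any effect on results cannot be derived; the ratios above are assumptions and show only that mixing can matter. Two further inferences should be avoided:

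- Benefit and harm do not cancel within a pooled stroke count, because there is no untreated arm. The issue is only that the two kinds of event may not be shown apart.
- The SAP is undated and written in the past tense, but this does not show that the outcomes were chosen after the data were seen. The documents are silent on timing.

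This is a cheap improvement, not a threat to the main result.

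**What to change.** In the SAP:

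1. Define stroke. By age group, report ischemic stroke, with counts of its three types, separately from non-traumatic hemorrhagic stroke.
2. State that a hemorrhagic stroke may also count as major bleeding, and how many do.
3. Report anticoagulation-related and cardiovascular deaths alongside all-cause mortality.
4. Give all of these as counts and proportions with exact 95% confidence intervals. No formal test of each subtype is needed.
5. Where an outcome is tested and expected counts fall below 5, use Fisher's exact test, or its Freeman-Halton extension for three groups, instead of chi-squared.
6. Name any Section 6 item that is deliberately dropped, and say why.

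The cost is small, because Section 6 already lists the categories. The attached follow-up form is not among the documents reviewed, so whether it records each category should be confirmed. Tables already produced would need some re-tabulation. Sparse categories will have wide intervals, cause of death will be less certain than death itself, and the exact test is more conservative than the planned one.

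### Three age groups are compared on TTR, but the only fitting test named is the two-group t test at P < .05, with no overall test, primary window, contrast or multiplicity rule

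*SAP*

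**What the plan says.** The SAP is a single paragraph. Its aim is to detect "differences in outcomes among age groups (70-79, 80-89, and 90+) undergoing anticoagulation therapy at study enrollment and in 6-month intervals for 24 months". On the main endpoint it states "The primary outcome of interest was time in therapeutic range (TTR", and defines TTR as the percentage of time that a patient's INR "values were in range over a 6-month period". It does not say which 6-month period. The testing rule is "Student t tests and chi-squared tests were conducted to compare data between groups". The threshold follows: "Statistical significance was set at" P < .05, with a 95% confidence interval. Tests are not assigned to outcomes.

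Protocol section 6 (Analysis Plan) asks for comparison by decade and lists "TTR for 2 years and best and worse 6 months". It does not rank these quantities or name a test. Protocol section 4.3 says "All patients aged 90 years or older who fit the criteria will be approached about participation in the study", and then "An equal number of patients from the ACS who are aged 80-89 years", with the same for ages 70-79. That makes 90+ the anchor for recruitment. Neither document makes it the reference group for analysis.

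**The concern.** A chi-squared test can handle three groups at once, but it is for categorical data. That leaves the t test for TTR, and one t test cannot answer a question about three groups. Several must be run, or one pair must be chosen, and the plan does not say which. The window is open in the same way: the SAP refers to repeated 6-month intervals, and the protocol adds a 2-year figure and the best and worst 6 months.

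The consequence is for interpretation. A reader who sees a TTR difference reported at P < .05 cannot tell whether it was the only test or one of a dozen (three pairs at four windows). With more than one contrast or window, the chance of at least one spurious age difference on the primary outcome exceeds .05.

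**Working it through.** **Inputs from the documents.** Three age groups (SAP); per-test threshold .05 (SAP); equal group sizes intended (protocol section 4.3). The documents give no sample size, power, TTR standard deviation or family-wise error target, so there is no stated figure to reproduce.

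**Assumptions.** Two-sided tests (sidedness is not stated), equal variances, and no true difference in mean TTR among the three groups.

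**One window, one named contrast.** 5.0%, by definition.

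**One window, 90+ versus each younger group.** The two differences share the 90+ mean. With equal group sizes their correlation is (σ²/n) / (2σ²/n) = 0.5. Then

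P(at least one P < .05) = 1 − P(|Z₁| < 1.96, |Z₂| < 1.96; correlation 0.5) = 0.0907.

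**One window, all three pairs.** At least one pair is significant when the studentized range Q of three means exceeds 1.96 × √2 = 2.77:

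P(Q > 2.77; 3 groups) = 0.1223.

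Simulated pooled-variance t tests with 10 to 100 patients per group gave 9.0-9.1% and 12.1-12.3%. Treating the tests as independent would overstate the risk: 1 − 0.95² = 9.75% and 1 − 0.95³ = 14.26%. With assumed unequal sizes (50:50:25, 50:50:100, 25:50:50) the results were 8.5-9.5% and about 12.1%.

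**Four post-enrollment windows (illustration only).** The documents do not say that every window was tested, and they give no within-patient correlation, so a range is assumed:

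| Assumed correlation | 90+ versus each | All three pairs |
|---|---|---|
| 0.9 | 17% | 22% |
| 0.5 | 27% | 34% |
| 0 | 32% | 41% |

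The zero-correlation row follows directly: 1 − (1 − 0.0907)⁴ = 0.316 and 1 − (1 − 0.1223)⁴ = 0.406. The other rows are simulated.

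**When one group truly differs.** Only one of the three pairs is then a true null, so the false-positive risk at one window is 5%. If the differing group is 90+, the two contrasts against 90+ contain no true null at all.

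**Check of the remedy.** The procedure is an overall Welch test at .05 on one TTR quantity, then pairwise Welch tests at .05 only if it is significant. If all means are equal, a false claim requires a false overall result, at about .05. If one group differs, one true-null pair remains, tested at .05. Simulation with assumed values (mean 65%, SD 15 points, normal and beta-distributed TTR, six size and SD settings) gave 4.8-5.2% with no difference, and 4.7-5.3% for the true-null pair when the third group differed by 20 points. With 1.5 times the SD in the smallest group, an ordinary F test gave 7.6-7.8% at 50/50/30 and 9.6% at 50/50/20, while Welch's test stayed at 4.8-5.1%.

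**The case against.** The strongest reply is that this is a prospective registry (protocol section 3) with no randomised comparison, confirmatory hypothesis, sample size or family-wise target. P < .05 can be read as a per-test threshold, and each t test keeps its 5% error under its own null. That stands. A reader might infer that the SAP breaks an error guarantee, but it never gives one. What remains is that the SAP itself declares a primary outcome and a significance threshold, and leaves the reader unable to judge a p value on that outcome.

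A second reply is that 9% and 12% hold only when all three means are equal. That is also correct, and the figures should always carry the condition.

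A third is that an overall test may have been run, or only one contrast at one window. Nothing in the documents excludes either. Stating it would settle part of the point at once, although the window would still need naming.

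Finally, Welch's advantage over the ordinary F test was shown under assumed sizes and SDs, whereas equal numbers were planned. Those settings are illustrative. Early withdrawal (protocol section 4.4) makes unequal sizes at analysis plausible, and Welch's test costs little if they stay equal.

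**Conclusion.** The point holds as a gap in the analysis of the primary outcome that should be fixed. The plan poses a three-group question about continuous TTR and names only a two-group test for it, with no overall test, window, contrast or multiplicity rule in either document.

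Under no true difference, equal group sizes and variances, and two-sided tests at one window, the chance of at least one P < .05 is about 9% for two contrasts against 90+ and 12% for all three pairs. Over four windows it would be about 17% to 41%, depending on the contrasts and the assumed correlation. That range is an illustration and is not a finding about this study.

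Two stronger readings are tempting and unsupported. One is that the study's false-positive rate is 12%, or 41%: the number of tests is not stated, so no actual rate can be derived. The other is that the recruitment plan fixes 90+ versus each younger group as the analysis: it suggests this, but neither document says so. Confidence is high in the omission and does not extend to any particular size of error.

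**What to change.** - **Primary quantity.** Name one 6-month post-enrollment TTR window, in line with the SAP's definition. If the protocol's 2-year TTR is preferred, first reconcile protocol section 6 with the SAP, because that would change the declared outcome.
- **Primary analysis.** Make one overall three-group Welch test at .05 the primary test. Claim pairwise Welch contrasts, each at .05, as significant only if the overall test is. Otherwise report pairwise differences with 95% confidence intervals and no significance claim.
- **Everything else on TTR.** Label the enrollment comparison, the other windows and the best and worst 6 months descriptive.
- **Disclosure.** The SAP is in the past tense, so label any reanalysis post hoc and report how many TTR tests were run, at which windows and for which contrasts. Claim about 5% family-wise error only if the TTR quantity was fixed without knowledge of the results; choosing it afterwards does not restore that rate.

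No new data are needed: the cost is revised SAP wording, one standard reanalysis and a count of tests. The downside is that some nominally significant pairwise or window results lose that status.
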